## **Systemic feature score**

For total score, summary statistics for the observed values and the change/percent change from baseline will be provided by scheduled visit.

For each component score, the number and percentage of participants whose score is 1 (present) will be provided by scheduled visit.

The total score will be calculated by summing the scores of each component and is defined as an integer value 0 to 10. The total score will be calculated only when all components are available.

Each component will be assigned a score of 1 (present) or 0 (absent) as follows:

- Fever [defined as a body temperature  $>37.5^{\circ}\text{C}$  at least once a day during at least 5 consecutive days]
- Rash [defined by the presence of typical salmon-pink rash on the trunk and elsewhere during the febrile episodes]
- Serositis
- Lymphadenopathy [defined by lymph node enlargement to  $>1.5$  cm localized anywhere within the body]
- Hepatomegaly and/or splenomegaly that had been confirmed by ultrasound evaluation

At baseline, laboratory features were considered present based on the following:

- ESR  $\geq 20$  mm/hour
- CRP (observed)  $\geq 10$  mg/liter
- White blood cell (WBC) count  $\geq 12 \times 10^9$ /liter
- Hemoglobin  $\leq 11$  g/dl
- Platelet count  $\geq 400 \times 10^9$ /liter.

During treatment epochs and at follow up visits, the laboratory parameters were scored as follows:

- ESR, score of 0 if  $<20$  mm/hour or if decreased by  $\geq 30\%$  compared to baseline, score of 1 if increased or if decreased by  $<30\%$  compared to baseline
- CRP, score of 0 if  $<10$  mg/liter or if decreased by  $\geq 30\%$  compared to baseline, score of 1 if increased or if decreased by  $<30\%$
- WBC count, score of 0 if  $<12 \times 10^9$ /liter or if decreased by  $\geq 20\%$  compared to baseline, score of 1 if increased or if decreased by  $<20\%$
- Hemoglobin level, score of 0 if  $>11$  g/dl or if increased by  $\geq 20\%$  compared to baseline, but score of 1 if decreased or if increased by  $<20\%$ ;
- Platelet count, score of 0 if  $<400 \times 10^9$ /liter or if decreased by  $\geq 20\%$  compared to baseline, score of 1 if increased or if decreased by  $<20\%$ .

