Key Inclusion criteria	
 • Signed informed consent must be obtained prior to participation in the study. • Japanese male/female participants aged ≥ 16 years • Confirmed diagnosis of AOSD as per Yamaguchi classification criteria (Yamaguchi M, 1992) with an onset of disease ≥ 16 years of age. • Active disease at the time of baseline defined as follows 
 - Fever (body temperature $> 38^{\circ}\text{C}$) due to AOSD for at least 1 day within 1 week before baseline - At least 2 active joints (tender or swollen) - CRP ≥ 10 mg/L • Participants who have history of inadequate response to more than 2 weeks of corticosteroids equivalent to at least 0.4 mg/kg/day of prednisolone
Key Exclusion criteria	
 • History/evidence of active MAS or disseminated intravascular coagulation (DIC) within 6 months of enrollment. • Underlying metabolic, renal, hepatic, infectious or gastrointestinal conditions which in the opinion of the investigator compromises the participant and/ or places the participant at unacceptable risk for participation in an immunomodulatory therapy. • Positive TB screening test (chest X-ray and Quantiferon TB test) at screening visit or within 4 weeks prior to the screening visit. • Active or recurrent bacterial, fungal or viral infection at the time of enrollment, including participants with evidence of Human Immunodeficiency Virus (HIV) infection, Hepatitis B and Hepatitis C infection. • History of malignancy of any organ system, treated or untreated, within the past 5 years, regardless of whether there is evidence of local recurrence or metastases, with the exception of localized excised non-melanomatous skin lesions.
Study treatment	Canakinumab 4 mg/kg (maximum of 300 mg) administered subcutaneously every 4 weeks at the study site throughout the study.
Treatment of interest	Canakinumab 4 mg/kg s.c (maximum of 300 mg) with stable dose of corticosteroids. Further details about the investigational treatment are provided in Section 6

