8.3.4 Systemic feature score

Systemic feature score consists of 5 clinical and 5 laboratory assessments. Clinical features include fever, rash, lymphadenopathy, hepatosplenomegaly and serositis. Laboratory features include erythrocyte sedimentation rate, C reactive protein, leucocyte count, hemoglobin level

and platelet count. Each clinical and laboratory feature will be assigned a score of 1 (present) or 0 (absent):

- Fever [defined as a body temperature $>37.5^{\circ}\text{C}$ at least once a day during at least 5 consecutive days]
- Rash [defined by the presence of typical salmon-pink rash on the trunk and elsewhere during the febrile episodes]
- Serositis,
- Lymphadenopathy [defined by lymph node enlargement to >1.5 cm localized anywhere within the body]
- Hepatomegaly and/or splenomegaly that had been confirmed by ultrasound evaluation

Note: Ultrasound sonography for liver and spleen must be performed at baseline, Week 28, Week 48 and EOS visit to assess the presence of hepatomegaly and splenomegaly.

At other assessment visits, palpation will be performed. In case investigator confirmed any findings of hepatomegaly/splenomegaly by palpation, perform ultrasound sonography. If no finding regarding hepatomegaly or splenomegaly is confirmed by palpation, hepatomegaly/splenomegaly is evaluated as “absent”. If there are any findings by palpation but ultrasound sonography is not performed, then hepatomegaly/splenomegaly will be evaluated as “present”.

At baseline, laboratory features were considered present based on the following:

- ESR ≥ 20 mm/hour
- CRP ≥ 10 mg/liter
- White blood cell (WBC) count $\geq 12 \times 10^9$ /liter
- Hemoglobin ≤ 11 g/dl
- Platelet count $\geq 400 \times 10^9$ /liter.

During treatment epochs and at follow up visits, the laboratory parameters were scored as follows:

- ESR, score of 0 if <20 mm/hour or if decreased by $\geq 30\%$ compared to baseline, score of 1 if increased or if decreased by $<30\%$ compared to baseline
- CRP, score of 0 if <10 mg/liter or if decreased by $\geq 30\%$ compared to baseline, score of 1 if increased or if decreased by $<30\%$
- WBC count, score of 0 if $<12 \times 10^9$ /liter or if decreased by $\geq 20\%$ compared to baseline, score of 1 if increased or if decreased by $<20\%$
- Hemoglobin level, score of 0 if >11 g/dl or if increased by $\geq 20\%$ compared to baseline, but score of 1 if decreased or if increased by $<20\%$;

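### The follow-up rules for the five laboratory items of the systemic feature score overlap: one value can qualify for both 0 and 1, and neither document says which prevails

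*SAP*

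**What the plan says.** Protocol 8.3.4 states that "Systemic feature score consists of 5 clinical and 5 laboratory assessments", each scored 0 or 1. SAP 2.7.2 adds that the total "is defined as an integer value 0 to 10" and is calculated only when every component is available.

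At baseline the laboratory items are scored by limits alone: ESR 20 mm/hour or more, CRP 10 mg/L or more, white cells 12 × 10⁹/L or more, hemoglobin 11 g/dl or less, platelets 400 × 10⁹/L or more.

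At follow-up each item has two separate definitions, the same in both documents:

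- **Score 0.** The value is on the normal side of the limit, or it has improved by a stated percentage. ESR is 0 if below 20 "mm/hour or if decreased by" at least 30%. Hemoglobin is 0 if above 11 "g/dl or if increased by" at least 20%.
- **Score 1.** For ESR the text continues "compared to baseline, score of 1 if increased or if decreased by" less than 30%. For hemoglobin it reads "compared to baseline, but score of 1 if decreased or if increased by" less than 20%. The limit does not appear in this clause for any of the five items.

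On reporting, the SAP says: "For total score, summary statistics for the observed values and the change/percent change from baseline will be provided by scheduled visit". The number and percentage scoring 1 on each component are also tabulated by visit. Change in the total and in each component is listed as a secondary endpoint in Protocol Table 2-1 and SAP Table 1-1. SAP 2.14 includes total and component scores in the output for the first 11 participants, and SAP 2.2.1 repeats them by prior tocilizumab use.

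**The concern.** A pair of definitions for a binary item should cover every value once. These two overlap wherever a follow-up value is on the normal side of its limit but has moved slightly from baseline. Normal hemoglobin, white cell and platelet values move slightly at most visits, so the overlap does not depend on unusual data.

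Baseline uses the limits alone, so an item that was never abnormal starts at 0. If the score-1 clause is applied literally, or is simply the last condition in the program, that item becomes present at follow-up although the value is still normal. Two programmers following the same text could produce different totals, changes from baseline and component counts from identical data. At stake is the reproducibility of a listed secondary endpoint in an analysis meant to support the registration dossier.

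**Working it through.** **1. The plan's own figure.** 5 clinical + 5 laboratory items, each 0 or 1, give a maximum of 10. This agrees with the stated range.

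**2. The rules as conditions.** Let b be baseline, f follow-up, c the limit and p the percentage. For ESR, CRP, white cells and platelets:

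- score 0 if f < c, or (f − b)/b ≤ −p
- score 1 if f > b, or f < b with (f − b)/b > −p

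For hemoglobin the directions are reversed. Both definitions apply when f is on the normal side, differs from b, and has not improved by p. Neither applies when f = b on the abnormal side (for example ESR 40 then 40, or hemoglobin 10 then 10), unless a 0% change is read as a small improvement.

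**3. Values normal before and after (illustrative).**

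| Item | c | p | b → f | Change | Meets 0 | Meets 1 |
|---|---|---|---|---|---|---|
| ESR | 20 | 30% | 10 → 12 | +20.0% | yes | yes |
| White cells | 12 | 20% | 7 → 8 | +14.3% | yes | yes |
| Hemoglobin | 11 | 20% | 13 → 12.5 | −3.8% | yes | yes |
| Platelets | 400 | 20% | 250 → 260 | +4.0% | yes | yes |

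The overlap also reaches items that were abnormal at baseline but close to the limit. White cells 13 → 11.5 is below 12 (score 0) and a fall of 1.5/13 = 11.5%, less than 20% (score 1).

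**4. CRP is bounded by an entry criterion.** Under "Active disease at the time of baseline defined as follows", Protocol 5.1 requires CRP of at least 10 mg/L, the same limit that scores CRP as present at baseline. A conflict then needs b ≥ 10, f < 10 and f > 0.7b. Hence 0.7b < 10, so b < 10/0.7 = 14.29 mg/L.

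- 12 → 9 (−25%): both definitions apply
- 15 → 9.9 (−34%): score 0 only
- 50 → 9 (−82%): score 0 only

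So for laboratory values normal both before and after, an eligible participant has at most 5 − 1 = 4 items in dispute.

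**5. The sign of the change can reverse.** Illustrative eligible participant, with the clinical items held constant:

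| Item | b → f | Baseline score | Follow-up, 0 prevails | Follow-up, 1 prevails |
|---|---|---|---|---|
| CRP | 100 → 2 | 1 | 0 | 0 |
| ESR | 80 → 10 | 1 | 0 | 0 |
| Hemoglobin | 13.0 → 12.5 | 0 | 0 | 1 |
| White cells | 9.0 → 8.5 | 0 | 0 | 1 |
| Platelets | 300 → 290 | 0 | 0 | 1 |
| Laboratory subtotal | | 2 | 0 | 3 |
| Change | | | −2 | +1 |

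Three disputed points in one such participant move the group mean by 3/11 = 0.27 in the first-11 analysis, or 3/14 = 0.21 with all 14 participants.

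**The case against.** The best defence is that only one reading gives every clause work to do. If the score-1 clause prevailed, the limits would matter only for a normal value exactly unchanged, and every other value would be scored on percentage change alone. The limits were evidently meant to act, the score-0 clause comes first in each line, and scoring a normal value as present contradicts the baseline rule. That argument stands as evidence of intent: score 0 was probably meant to prevail. But neither document says so, the score-1 clause is unconditional, and the conjunction in the hemoglobin line can be read as overriding what precedes it. The argument also leaves open how an unchanged abnormal value is scored.

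The consequence is limited, and that too stands. The score has no hypothesis test and enters neither the adapted ACR 30 response nor the tapering criteria. Component counts, CRP and hematology values are all tabulated by visit, so with 14 participants normal values scored as present could be noticed.

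A reader might infer that a participant with all five laboratory items normal throughout could move from 0 to 5. The entry criterion on CRP rules this out for anyone eligible. Five disputed points need four items normal throughout plus a CRP falling from between 10 and 14.29 to below 10 by less than 30%; CRP was then not normal at baseline. A participant treated in breach of the CRP criterion would stay in the FAS, but that is a deviation, not the planned population.

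**Conclusion.** The point holds as a defect of specification. The five follow-up laboratory rules are not mutually exclusive, have no stated precedence, and strictly leave an unchanged abnormal value unscored. If such an item were programmed as missing, the total for that visit would be missing too.

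For an eligible participant the ambiguity is up to 4 of 10 points from items normal before and after. CRP adds to it only in the narrow band above. It can reverse the sign of an individual's change in total score and alters the component counts directly.

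This rests on a literal reading of both clauses and on the observed CRP value being used at follow-up as at baseline. The laboratory values in the examples are illustrative. How often the overlap would occur, and how far the mean would shift overall, cannot be stated, because the documents give no laboratory distributions; any such figure would reflect assumed inputs. Nor do the documents support an inference that the primary result or the key secondary tapering endpoint is affected.

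**What to change.** Add one sentence to SAP 2.7.2: at follow-up a laboratory item scores 1 only if neither score-0 condition is met, and 0 otherwise. Spelled out, 1 requires the value to be at or beyond the abnormal limit (ESR ≥ 20, CRP ≥ 10, white cells ≥ 12, hemoglobin ≤ 11, platelets ≥ 400) and not to have improved by the stated percentage. This removes the overlap, closes the gap for unchanged abnormal values and matches the baseline limits. Check the scoring program, and any output already produced, against the sentence.

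The cost is a SAP clarification and a program check, with no new data. A protocol change needs a written amendment with IRB/IEC approval and, where required, health authority approval (Protocol 14.1). The wording in Protocol 8.3.4 can therefore be aligned at the next amendment; it does not justify one on its own.

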### **2.7.3 Handling of missing values/censoring/discontinuations**

For the adapted ACR 50/70/90/100 at Week 8, the same handling of intercurrent events and missing values will be applied as for the adapted ACR 30.

For other endpoints, imputation of missing values will not be performed, and all endpoints will be tabulated based on observed data.

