9.1 Discontinuation from study treatment and from study

9.1.1 Discontinuation from study treatment

Discontinuation of study treatment for a participant occurs when study treatment is permanently stopped for any reason (prior to the planned completion of study treatment administration, if any) and can be initiated by either the participant or the investigator.

The investigator must discontinue study treatment for a given participant if, he/she believes that continuation would negatively impact the participant's well-being.

Discontinuation from study treatment is required under the following circumstances:

- Participant/guardian decision
- Pregnancy
- Use of prohibited treatment as per recommendations in the prohibited treatment section
- Any situation in which continued study participation might result in a safety risk to the participant
- Any severe or serious adverse event that is not compatible with administration of study medication, including adverse events that require treatment with an unacceptable co-medication
- Onset of malignancy
- Occurrence of uncontrolled life-threatening infection
- Any other protocol deviation that results in a significant risk to the participant's safety

The investigator should consider discontinuing participants from study treatment who experience a clinically important worsening of disease activity compared to baseline at two consecutive visits after Week 4. A clinically important worsening will be defined as participants who do not meet the adapted ACR30 criteria by Week 12 or participants with non-response (defined as Adapted ACR <30) at two consecutive visits at any time in the study beginning at Week 12.

All participants who discontinue will complete an EOS visit, be discontinued from the trial and be treated as per standard local medical practice (see also [Section 10.1.3](#) for information on SAE reporting following the last dose of study medication).

If discontinuation from study treatment occurs, the investigator should make a reasonable effort to understand the primary reason for the participant's discontinuation from study treatment and record this information.

Participants who discontinue from study treatment agree to return for the end of treatment and follow-up visits indicated in the Assessment Schedule (refer to Section 8).

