### **2.5.4 Handling of missing values/censoring/discontinuations**

Missing adapted ACR 30 assessment at Week 8 will be imputed with non-responder regardless of the reason for missing data (non-responder imputation).

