### **Adapted ACR 30/50/70/90/100 response criteria**

The adapted ACR 30/50/70/90/100 at Week 8 and the adapted ACR 30/50/70/90/100 at each visit including Week 8 will be analyzed separately.

For the adapted ACR 50/70/90/100 at Week 8, the primary analysis will be repeated as performed for adapted ACR 30 except the statistical hypothesis testing. The results will be presented with the primary analysis of the adapted ACR 30. In addition, the adapted ACR 30/50/70/90/100 response at Week 8 will be summarized with the number and percentage of participants by the subgroups described in Section 2.2.1.

For the adapted ACR 30/50/70/90/100 at each visit, frequency tables with the number and percentage of participants achieving the adapted ACR 30/50/70/90/100 criteria will be provided by scheduled visit.

The line plot of the percentage of participants achieving the adapted ACR 30/50/70/90/100 response for each visit will be provided.

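### By-visit adapted ACR response is tabulated on observed data although the protocol advises considering a treatment stop for non-responders from Week 12, so later response rates are likely to be biased upward

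*SAP*

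**What the plan says.** **Week 8.** SAP 2.5.4 uses non-responder imputation for the primary endpoint: "Missing adapted ACR 30 assessment at Week 8 will be imputed with non-responder regardless of the reason for missing data". SAP 2.7.3 extends the ACR 30 handling of intercurrent events and missing values to ACR 50, 70, 90 and 100 at Week 8.

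**Other visits.** SAP 2.7.2 separates two analyses: "The adapted ACR 30/50/70/90/100 at Week 8 and the adapted ACR 30/50/70/90/100 at each visit including Week 8 will be analyzed separately". For the by-visit analysis, "frequency tables with the number and percentage of participants achieving the adapted ACR 30/50/70/90/100 criteria will be provided by scheduled visit", together with a line plot. SAP 2.7.3 then covers everything outside the Week 8 exception: "For other endpoints, imputation of missing values will not be performed, and all endpoints will be tabulated based on observed data". No by-visit version with non-responder imputation is planned.

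**Stopping and follow-up.** Protocol 9.1.1 states: "The investigator should consider discontinuing participants from study treatment who experience a clinically important worsening of disease activity". It defines such worsening as not meeting ACR 30 by Week 12, or as non-response "at two consecutive visits at any time in the study beginning at Week 12". It says that all who discontinue complete an end-of-study (EOS) visit and are discontinued from the trial. It also says that participants who stop treatment agree to return for follow-up visits. The minimum data listed for abbreviated visits after a treatment stop are new or concomitant treatments and adverse events.

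**Mapping.** SAP 2.1.2 and 2.14 remap the EOS visit of an early discontinuer to the window of one scheduled visit.

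**The concern.** The criterion that prompts an investigator to consider stopping treatment is the same ACR 30 response that the by-visit tables report. Where that advice is followed and the participant leaves the trial, the failing value appears once, at the remapped EOS visit, and no value follows. A percentage based on the remaining participants then describes response among those not yet removed, many of whom remain because they responded.

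The Week 28 and Week 48 analyses support and supplement the registration dossier. By-visit ACR response and its line plot are on the SAP 2.14 list for the first 11 participants, and SAP 2.2.1 repeats by-visit ACR response by prior tocilizumab use, where denominators are smaller still. The trial has one arm, so no control group shows the same attrition. A curve that rises because failures have left could be read as deepening or durable response.

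**Working it through.** The plan gives no by-visit response rate or discontinuation rate, and the sample size section is redacted, so there is no stated figure to reproduce.

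**Step 1: which rule applies.** The only exception to observed-data tabulation is the Week 8 analysis. The by-visit ACR analysis is declared separate from it, so its tables and plot, including their own Week 8 row, are tabulated on observed data.

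**Step 2: are later ACR values expected after a stop?** Protocol 9.1.1 has one sentence that ends trial participation after EOS and another that provides for follow-up visits. Protocol Section 3 describes only a screening and a treatment epoch, and the minimum data listed in 9.1.1 contain no ACR components. Later ACR values are therefore not assured.

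**Step 3: arithmetic.** Inputs from the SAP: n = 14 for secondary endpoints (2.7.2) and about 11 for the first-participants analysis (2.14). Assumptions, not in the documents: r responders, k non-responders who leave, nobody changes status and no responder leaves.

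- Observed-data rate: r/(n − k)
- Full-FAS rate with leavers as non-responders: r/n
- Difference: r/(n − k) − r/n = rk/[n(n − k)], which is never negative

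| k | n = 14, r = 8 (full FAS 8/14 = 57.1%) | n = 11, r = 6 (full FAS 6/11 = 54.5%) |
|---|---|---|
| 1 | 8/13 = 61.5% | 6/10 = 60.0% |
| 2 | 8/12 = 66.7% | 6/9 = 66.7% |
| 3 | 8/11 = 72.7% | 6/8 = 75.0% |
| 4 | 8/10 = 80.0% | 6/7 = 85.7% |

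Rise in percentage points over a range of r:

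- n = 14, r from 6 to 11: one leaver 3.3 to 6.0, two 7.1 to 13.1, three 11.7 to 21.4.
- n = 11, r from 4 to 9: one leaver 3.6 to 8.2, two 8.1 to 18.2. Three leavers, with r from 4 to 8: 13.6 to 27.3.

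**Step 4: expected value.** Let p be the true response proportion and q the probability that a non-responder leaves. The expected observed-data rate is p/[p + (1 − p)(1 − q)]; exact binomial enumeration at n = 11 and n = 14 agrees. For p = 0.60 and q = 0.50 this is 0.60/(0.60 + 0.40 × 0.50) = 0.60/0.80 = 75.0%. With the same q, p = 0.50 gives 66.7% and p = 0.70 gives 82.4%. If responders also left with probability q, the factor (1 − q) would cancel and the result would be p. The upward bias thus comes from non-responders leaving more often than responders, which is what the 9.1.1 advice makes likely.

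**The case against.** Several points on the other side have force.

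- **The stopping text is advisory.** Investigators are asked to consider stopping. Participant choice, adverse events, prohibited medication and missed visits also produce missing data. A reader might infer that the rates must rise, or that all missingness is caused by non-response; the documents support neither. They do support a likely link between the two.
- **The denominator is not stated.** SAP 2.7.2 summarises efficacy endpoints on the FAS. If percentages were taken over the FAS count, missing participants would already count as non-achievers and the rise would vanish. The observed-data wording of 2.7.3 points the other way, but the SAP should settle it.
- **Follow-up may continue.** One sentence in Protocol 9.1.1 and one in Section 8 provide for visits after a treatment stop. They conflict with the sentence on leaving the trial, so continued ACR data cannot be ruled out or relied on.
- **EOS remapping keeps the failure.** It does so for one visit, which delays the rise without preventing it.
- **The tables are descriptive.** They carry no test. The key secondary tapering endpoint at Week 28 also requires maintained ACR 30, and SAP 2.3.1 tabulates discontinuations with reasons. This limits the consequence but does not correct the percentages or the plot.

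A reader might also infer that the report will show two different Week 8 ACR 30 rates. It can, but only if a Week 8 value is missing or a Week 8 responder had a steroid increase or intravenous steroid.

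**Conclusion.** The point holds as a likely upward bias in the by-visit ACR 30 to 100 tables and line plot after Week 12, with no planned analysis to show its extent. It rests on three readings: observed data means a denominator of participants with a value, some investigators act on the 9.1.1 advice, and those who stop give no ACR values after EOS.

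The size is unknown because the documents give no stopping rate. Over the assumed ranges in the working, one departing non-responder adds about 3 to 8 points and two add about 7 to 18. Extreme cases should not be taken as forecasts: with 11 participants and 7 responders, 7/7 = 100% against 7/11 = 64% requires all four non-responders to stop.

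The primary test and the separate Week 8 ACR 50 to 100 analysis use non-responder imputation and are not affected.

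**What to change.** In SAP 2.7.3:

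1. Present by-visit adapted ACR 30/50/70/90/100 over the full FAS denominator. Use the remapped EOS value at its own visit, and count participants as non-responders at any visit where they have discontinued or have no value.
2. Base the line plot on this version.
3. Keep the observed-data table as supportive, state its denominator, and show the number observed at each visit.
4. Do not carry the pre-Week-8 steroid-increase rule to other visits. An increase at Week 6 would retrospectively fail a Day 15 response, and increases after Week 8 would still be ignored. Without that rule, the Week 8 ACR 30 row follows the handling of the supplementary analysis in SAP 2.5.5, and a footnote should say why it can differ from the primary result.

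In Protocol 9.1.1, reconcile the sentences on leaving the trial and on returning for follow-up visits, since they decide whether later ACR data exist. No view is taken here on the stopping advice itself.

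The cost is SAP wording, one extra table version and lower later-visit rates. An isolated missed visit would count as a failure in the non-responder version; the observed-data table beside it offsets this.
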